Procedure. The new booster seat information material will be created by taking Transport Canada's⁴⁴ online material (click here to open link) and then by adding an introduction that explains: (a) seatbelts redirect crash forces to the child's thorax and pelvis; (b) booster seats ensure children wear the seatbelt correctly across the hips and chest; and (c) booster seats, used in combination with the seatbelts, prevent injuries to head, neck, spine, abdomen, internal organs, as well as injuries resulting from ejection. See Appendix 1. Three focus group interviews (one with fathers only, one with mothers, and one mixed) will be conducted to test the enhanced material. Focus group discussions will revolve around knowledge and beliefs about booster seats and seatbelts, as well as opinions regarding the content, wording, and format of the education material.

Analysis. The focus group interviews will be audio recorded and participants' feedback will be used to improve the material's *concept* (i.e., whether the message produced the intended effect) and *execution* (i.e., whether the material effectively conveys the intended message), as appropriate.

Randomized Controlled Trial

Objective. To determine if the enhanced Transport Canada online material is better than the current version at increasing perceived safety benefit and intention to use booster seats.

Design. An internet-based Phase II proof-of-concept trial (with a control group) will be conducted, in order to test if the intervention produces the intended psychological effect. The trial will use a concurrent two-group parallel randomized controlled design. The use of a control group is necessary to address threats to validity stemming from repeating observations on the same participants: learning and carry-over (i.e., learning something in the first question that then informs subsequent answers), sensitization (i.e., becoming more sensitive to differences by subsequent questions), and demand effects (i.e., noticing that the researcher wants a different response in the second question).

Randomization. Randomization schedule will be generated using the sealedenvelop.com. Randomization will be stratified by province, gender, and socioeconomic status. Additionally, randomization will be blocked to ensure balanced groups throughout allocation.

Blinding. Both researchers and participants will be blinded to allocation, even during data analysis.

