Participants. 303 mothers and 303 fathers of children 4 to 8 years old residing in any Canadian province, who speak English and drive with their child at least once a month. Participants will be excluded if their child has a physical condition that requires special transportation. Parents will be invited to participate, irrespective of whether they use booster seats always, occasionally, or never. A sample of 606 participants provides sufficient power to detect a mean difference of 0.4 points in the Benefit subscale of the BSAS. This difference in benefit scores has been found to distinguish those parents who consistently restrain their child in booster seats from those who do not. Sample size was estimated with the TwoSampleMean function for trials that test superiority of interventions (TrialSize package for R). Participants in the trial will receive \$1/each for the completion of the survey. Based on information from studies with similar characteristics, the expected response rate is 40%.

Setting and Procedures. The trial will be conducted entirely online. The online trial will be pilottested with a sample of 10 parents, recruited through the same procedure used for the focus groups. Each participant will be asked to complete the online trial, in the presence of a researcher, at their home, office, or the researcher's lab located in the BC Children's Hospital. Each participant will be asked to speak out loud as he or she navigates the online trial. The researcher will ask probing questions if participants understand the question in an unintended way, do not understand what they are supposed to do, move the mouse erratically, or express frustration and/or confusion. Participants will then be debriefed to identify any potential misunderstanding of the information provided (e.g., incorrectly inferring that seatbelts are inherently dangerous for children rather than necessary safety devices that must be used in combination with booster seats). At the end of the pilot test, participants will receive \$40/each. The online questionnaire and education material will be improved or corrected, as appropriate.

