After pilot-testing is complete, participants will be recruited through an online market research firm, Maru/Matchbox, which maintains a nationwide panel of 130,000 individuals whose distribution represents the Canadian population. Maru/Matchbox will send an email invitation to participate along with a link to the online survey. The landing page of the survey will provide description of the study for parents to read. The online survey will be set up in such a way that participants won't be able to start answering questions, unless they consent by clicking the "I

agree" button. Participants, will be advised to print and keep a copy of the consent form either as PDF or as hard copy. After consenting to participate, the online trial will proceed as follows:

- 1. Participants will complete a demographics questionnaire, the BSAS, and four questions on booster seat guidelines (e.g., minimum and maximum ages, heights, and weights to determine when a child should use a booster seat, and when it is safe for a child to use only the seatbelt).
- 2. The system will randomly assign the participant to either the intervention or the control group. Randomization will be stratified by sex, child age, and jurisdiction to ensure both groups are equal. This stratification is necessary because, in Canada: (a) fathers and mothers differ in their attitudes regarding child vehicle safety,⁴⁵ (b) booster seat use decreases as the child gets older,⁴⁶ and (c) provinces differ from one another in terms of legislation and booster seat education programs.⁴⁷
- 3. Participants in the intervention group will be presented the enhanced booster seat material, while participants in the control group will be presented the current Transport Canada booster seat material. Material provided to both groups will be stripped of logos (Transport Canada logos and corporate identity), but will be properly cited.
- 4. Participants will complete again the BSAS and the questions on booster seat guidelines.
- 5. Participants in the intervention group will be asked one or two multiple choice questions to ensure they did not misunderstood the information in an unintended way. These questions will be designed based on the information on adverse effects collected during the focus groups and the trial's pilot. If a parent answers incorrectly, the system will clarify the information immediately after.

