- 6. Participants in the control group will be given the option to view the enhanced booster seat material, in order to give them the opportunity to benefit from the intervention.

Analysis. The online version of the Booster Seat Attitudes Scale will be factor-validated and Cronbach's alpha of each BSAS subscale will be calculated to determine reliability. The effect of the intervention on the Benefit, Intention, and Self-Efficacy subscales of the BSAS will be examined through linear mixed effects models with random effects by province (to account for between-province differences in legislation and booster seat education programs). Multiple imputation will be used to address missing data. Intention-to-treat analysis will be conducted, by doing two separate analyses: one with the entire sample of participants and one with only participants who complete the trial. In addition, mediation analysis will be conducted to determine if perceived safety benefit mediated the effect of the intervention on intent to use booster seats. Dropout curves will be used to examine in which part of the trial participants in each condition were more or less likely to drop out. *Student's t, Wilcoxon Sign and Rank*, or *Mann-Whitman's U* tests will be used to compare, across groups, subjective estimates of the impact of the intervention on other parents, time spent reading the material, number of clicks on links to additional booster seat information, and pre- versus post-intervention difference in subjective estimates of the risk reduction afforded by booster seats and by seatbelts.

UPDATE 27 OF JUNE 2019:

Increase in perceived safety benefit of booster seats (primary outcome) and increase in intention to use booster seat (a secondary outcome) were evaluated by, first calculating the difference between the post-intervention score and the pre-intervention score for each participant. This difference was then compared with t tests (two-tailed). Parents' judgments of the impact of the intervention on their peers (a secondary outcome), which was assessed post-intervention only, was compared across study arms with the t tests (two-tailed). The same statistical analysis was used to evaluate the other secondary outcomes (parents' recall of booster seat information, Interest in booster seat information).

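### The plan gives two different lists of stratification factors, and the t tests of the 27 June 2019 update adjust for none of them

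*Combined protocol and SAP*

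**What the plan says.** All places are in the combined protocol and SAP, under Randomized Controlled Trial.

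- **Randomization:** "Randomization will be stratified by province, gender, and socioeconomic status", followed by "Additionally, randomization will be blocked to ensure balanced groups throughout allocation". No block size or factor levels are given.
- **Setting and Procedures, step 2:** "Randomization will be stratified by sex, child age, and jurisdiction to ensure both groups are equal". This step gives a reason for each of its three factors and does not mention socioeconomic status.
- **Analysis, original text:** the effect on the "Benefit, Intention, and Self-Efficacy subscales of the BSAS will be examined through linear mixed effects models with random effects by province". Province is the only stratification factor named. Judged impact on other parents was planned from the start as a simple two-group comparison.
- **Analysis, update of 27 June 2019:** for the post-minus-pre change in perceived benefit and intention, "This difference was then compared with t tests (two-tailed"). Judged impact on peers, measured after the intervention only, "was compared across study arms with the t tests (two-tailed"). For the rest, "The same statistical analysis was used to evaluate the other secondary outcomes". No covariate or stratum term appears, and the mixed model is neither kept nor withdrawn.
- **Participants:** "A sample of 606 participants provides sufficient power to detect a mean difference of 0.4 points in the Benefit subscale of the BSAS". Alpha, numerical power and standard deviation are not stated.

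**The concern.** There are two linked problems.

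First, each list of factors reads as complete, and the two differ in the third factor. A reader cannot tell what was balanced by design, so the randomization cannot be described accurately and the covariates for an adjusted model cannot be fixed.

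Second, the trial stratifies on factors that step 2 itself treats as related to attitudes or booster seat use, and then leaves them out of the analysis. Stratified allocation removes between-stratum variation from the true sampling error of the treatment difference. A plain t test still counts that variation in its standard error. If the strata predict the outcome, the reported intervals are wider than they need be and the test is conservative.

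**Working it through.** **1. The two lists side by side**

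| Randomization paragraph | Setting and Procedures, step 2 |
|---|---|
| province | jurisdiction |
| gender | sex |
| socioeconomic status | not listed |
| not listed | child age |

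Reading province as jurisdiction and gender as sex, the conflict is confined to socioeconomic status and child age. All four factors may have been used, but the plan does not say so. The 27 June 2019 updates revise outcomes, analysis and missing-data handling and leave both sentences as they are.

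**2. The plan's own sample size**

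The figure of 606 can be neither reproduced nor refuted. Equal allocation is implied by the ethics section, where half the participants do not receive the intervention, so take 303 per arm. Solving backwards at two-sided 5%, SD = 0.4 / [(1.96 + z_power) × sqrt(2/303)], which gives 1.757 at 80% power, 1.519 at 90% and 1.366 at 95%. Since the nominal power is unknown, all three are carried below. The result depends on nominal power and R², not on the SD itself.

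**3. Cost of ignoring the strata, under perfect balance**

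Let R² be the share of outcome variance explained by the strata, k = sqrt(1 − R²), z = 1.96 and d = z + z_power.

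- Alpha of the unadjusted test = 2[1 − Φ(z/k)]
- Interval excess = 1/k − 1
- Unadjusted power = Φ((d − z)/k)
- Adjusted power = Φ(d/k − z)

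Example with R² = 0.20 and 80% nominal power: k = 0.894 and d = 2.802. Alpha = 2[1 − Φ(2.191)] = 0.0284. Interval excess = 11.8%. Unadjusted power = Φ(0.941) = 0.827. Adjusted power = Φ(1.172) = 0.879. The gain is 5.28 points before rounding.

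| R² | Unadjusted alpha | Interval excess | Gain in points at 80% | at 90% | at 95% |
|---|---|---|---|---|---|
| 0 | 5.0% | 0% | 0 | 0 | 0 |
| 0.02 | 4.77% | 1.0% | 0.55 | 0.34 | 0.20 |
| 0.05 | 4.43% | 2.6% | 1.37 | 0.83 | 0.47 |
| 0.10 | 3.88% | 5.4% | 2.72 | 1.58 | 0.86 |
| 0.20 | 2.84% | 11.8% | 5.28 | 2.79 | 1.37 |

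**4. Simulation with incomplete blocks**

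Many small strata leave blocks unfilled, so balance is not perfect. The simulation used 606 participants and 20,000 runs per cell. It assumed permuted blocks of 4, ten provinces of unequal size, and additive factor effects with equal variance shares; mothers and fathers were equal in number. The strata number 40 (10 × 2 × a two-level third factor), 100 (10 × 2 × 5 single years of child age) or 200 (all four factors). At R² = 0.20:

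| Strata | Unadjusted alpha | Adjusted alpha | Interval excess | Power at 80% nominal, unadjusted / adjusted | Gain in points at 80% / 90% / 95% |
|---|---|---|---|---|---|
| 40 | 3.04% | 5.1% | 11.6% | 82.5% / 87.8% | 5.4 / 2.9 / 1.5 |
| 100 | 3.09% | 4.7% | 11.4% | 82.0% / 87.6% | 5.6 / 2.9 / 1.6 |
| 200 | 3.29% | 5.1% | 11.3% | 81.8% / 87.3% | 5.5 / 3.1 / 1.7 |

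Gains were taken before rounding. At R² = 0.05 the unadjusted alpha is 4.5%, 4.6% and 4.3%, and the gain at 80% nominal power is 1.3, 1.1 and 1.3 points. Simulation error is about 0.12 to 0.15 points for alpha and 0.27 for power near 82%. Imperfect balance moves alpha back toward 5% and lowers unadjusted power by up to about 1 point against the formula; the picture does not change.

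**5. If the third factor was not stratified**

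An unstratified factor differs between arms only by chance, with standard error sqrt(2/303) = 0.081 SD.

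**The case against.** The strongest reply is that nothing here endangers a conclusion. An unadjusted t test after stratified randomization is a common, valid and conservative choice. The R² ceiling of 0.20 has no anchor in the documents. The reasons given for stratifying concern levels of attitude and use, whereas the primary analysis is of change, and differencing removes stratum differences that are constant from before to after. At R² of 0.05 or less the gain is at most 1.4 points. The update is also written in the past tense, so results already existed. Adjusted models now would add about eight post hoc results: six subscales, recall and interest.

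Most of this stands, and it limits the size of the point. It does not remove it. Differencing gives no protection to outcomes measured only after the intervention, such as judged impact on peers. A small efficiency gain also does not settle the contradiction between the two lists, or the unexplained status of the mixed model. The multiplicity worry is met by keeping the t tests as the main results and labelling the adjusted models plainly.

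**Conclusion.** The concern holds in both parts: the two descriptions of the stratification disagree on the third factor, and the updated t tests use no stratification factor. It should be corrected, but it does not threaten the trial's validity. There is no bias, and type I error is at or below 5%.

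Assuming two-sided 5% and R² from 0 to 0.20, the unadjusted intervals are 0 to 12% too wide. Under balanced strata the forgone power is 0 to 5.3 points at 80% nominal power, 0 to 2.8 at 90% and 0 to 1.4 at 95%. With incomplete blocks the simulated maxima are 5.6, 3.1 and 1.7 points. For the change scores the low end is more plausible and the gain may be close to nil. R², alpha, nominal power, block size, factor levels and province sizes are all assumptions, because the plan gives none of them. For judged impact on peers no adjustment was dropped, since none was ever planned.

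**What to change.** 1. Reconcile the Randomization paragraph and step 2 of Setting and Procedures to the scheme the survey system actually ran, whether one list or all four factors. Give the levels of each factor and the block size.
2. State whether the mixed model with province random effects was kept or withdrawn.
3. Keep the t tests as the main results. Beside each, report the same outcome (change score or post-only score) from a linear model with main effects of the factors actually used, with province fixed or random. Label it as added after the original analysis. Adjustment for the baseline score is a separate question and is not part of the figures above.

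The cost is a corrected sentence, a statement on the mixed model, and one regression per outcome. The system needed each participant's stratum to allocate, so the data should be on record. Even with all four factors, at assumed levels of 10 provinces, 2 sexes, 5 ages and 2 socioeconomic groups, the model needs 9 + 1 + 4 + 1 = 15 stratification terms, or 17 parameters with intercept and treatment, for 606 participants. The drawbacks are a little more analysis and its post hoc status.

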The trial phase also poses minimal risk to participants. There is no known physical risk. In addition, psychological risks are not greater than the risk parents experience when looking at information on booster seats, because the information provided to the control and intervention groups is available to any parent interested in booster seat information. Social risks are less of a problem, given that the survey will be conducted entirely online. It is conceivable that a small number of participants may incorrectly interpret the information as "seatbelts are unsafe." However, any potential of misapprehension of the information provided to the control or the intervention group will be reduced during in the development phase and during pilot testing.

Finally, the trial design implies that half of the participants will not be exposed to a potentially beneficial intervention. To remedy this problem, participants in the control group will be exposed to the intervention after they complete the trial. The same safeguards to prevent misinterpretation will be applied to them.

Knowledge Translation potential

Findings from the present study can be quickly implemented in many settings, considering how ubiquitous the internet is and how fast the information online can be updated. Transport Canada, Parachute, BCAA, and Saskatchewan General Insurance, ICBC, and any other stakeholder with online presence can enhance their booster seat information page, by adding

the proposed intervention. Furthermore, pediatricians, family doctors, and emergency physicians, who often give safety advice to parents,⁴⁹ can also use this information by providing parents with a link to any aforementioned websites. In terms of knowledge translation, the most useful feature of the intervention is that information about how seatbelts and booster seats prevent injuries remains true regardless of legislation differences between jurisdictions. Thus, the potential impact of this research extends across provinces, countries, and continents.

An important advantage of the narrow scope I adopted here is that I am developing and testing a psychological principle that can be applied in different contexts: if the present study successfully and safely demonstrates that explaining the concept of redirecting crash forces increases perceived benefit and intention to use booster seats, then the same principle can be tested in face-to-face child seat clinics or social marketing campaigns.

Budget

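### Step 6 offers control parents the enhanced page with no misunderstanding check, while the ethics section says they will have the same safeguards as the intervention group

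*Combined protocol and SAP*

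**What the plan says.** Setting and Procedures lists six steps for the online trial. The Booster Seat Attitudes Scale and the guideline questions are completed before the material is shown and again at step 4. Step 5 then provides a check on comprehension: "Participants in the intervention group will be asked one or two multiple choice questions to ensure they did not misunderstood the information". It adds: "If a parent answers incorrectly, the system will clarify the information immediately after". Step 6 closes the list: "Participants in the control group will be given the option to view the enhanced booster seat material". It gives the purpose as letting controls share in any benefit, and mentions neither questions nor clarification.

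Ethical considerations describes the same stage differently. On the risk of misreading it says: "It is conceivable that a small number of participants may incorrectly interpret the information as" a message that seatbelts themselves are unsafe, and that this potential, for the material given to either group, "will be reduced during in the development phase and during pilot testing". On withholding the intervention it says: "participants in the control group will be exposed to the intervention after they complete the trial". The next sentence reads: "The same safeguards to prevent misinterpretation will be applied to them". The section does not list those safeguards or name the step 5 questions.

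**The concern.** The plan itself identifies a way in which the enhanced page could mislead: a parent might conclude that seatbelts are dangerous rather than that they must be combined with a booster seat. That risk comes from the content of the page, so it follows the page to whichever arm reads it. In the intervention arm, step 5 detects and corrects a misreading before the parent leaves. In the control arm, step 6 provides the same page and the procedure ends there.

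An online survey is normally programmed from the numbered steps. If that was done here, a protection stated in the ethics section would be missing in operation for half of the participants. What is at stake is participant protection and the accuracy of an ethics statement. The estimate of the treatment effect is not at stake.

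**Working it through.** No power, error-rate or event figure bears on this point, so the check is a comparison of the text.

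**1. Who receives the check.** Step 5 names the intervention group. Step 6 concerns the control group and contains no check. No later step exists.

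**2. What the ethics section commits to.** It makes two statements about controls, and each differs from step 6:

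| Item | Step 6 | Ethical considerations |
|---|---|---|
| Access to the enhanced page | Optional | Stated as something that will happen |
| Safeguard against misreading | None written | The same safeguards |

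**3. What the safeguards most naturally are.** The documents describe two kinds of protection: work on the material before launch (focus groups, and a think-aloud pilot with debriefing), and the step 5 questions with clarification. Three features of the text point to the second kind.
- The ethics section has already said, one paragraph earlier, that development and piloting cover the material given to either group. If the later sentence meant only that, it would add nothing.
- The later sentence speaks of safeguards applied to the control parents. Development and piloting act on the material beforehand. Step 5 is the only safeguard against misinterpretation in the documents that is applied to trial participants.
- Step 5 says that its questions will be built from adverse effects found in the focus groups and pilot. The plan therefore uses step 5 to deal with whatever misreading remains after that work.

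**4. Size.** The planned sample is 606, and the ethics section says that half will not receive the intervention during the trial: 606 / 2 = 303. About 303 is the ceiling on control parents who could be offered the page. The number who leave with an uncorrected misreading would be 303 × (share who open the page) × (share of those who misread it). The documents give neither share, so the product cannot be evaluated.

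**5. Effect on results.** The scale and the guideline questions are repeated at step 4, before step 6, and the ethics section places control exposure after completion of the trial. Viewing the page at that point cannot alter the between-arm comparison.

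**The case against.** The strongest reply has four parts.

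*The ethics section never names the step 5 questions.* This is correct. The only safeguards it names are development and pilot testing, which already cover the page whoever reads it. A reader might infer that the section expressly promises control parents the step 5 check. It does not. That reading is the more natural one for the reasons above, but it remains an inference. The ambiguity is itself a reason to define the term.

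*The ethics section is part of the plan, so the plan taken as a whole may already require the check.* This also stands in part. The documents do not establish that control viewers went unchecked. They show that the commitment is absent from the steps that would be programmed, and that step 5 is expressly limited to the other arm.

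*The page is tested before launch.* Three focus groups review it, and ten pilot parents think aloud and are debriefed for this very misunderstanding, after which the material is corrected as needed. This is real protection and control viewers would have it. It does not replace an individual check. If none of the ten pilot parents misread the page, the one-sided 95% upper limit on the misreading rate from the pilot alone is 1 − 0.05^(1/10) = 25.9%. The plan itself adds step 5 after this testing.

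*It may be too late.* The updates dated 27 June 2019 under Analysis report the analyses in the past tense, which suggests that data collection may be over. If so, a new survey branch would help nobody, and the remedy becomes an accurate statement of what was done.

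The difference between optional viewing and definite exposure is, taken alone, a small matter of wording.

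**Conclusion.** The concern holds as a conflict between the procedure and the ethics section. Steps 5 and 6 confine the misunderstanding questions and clarification to the intervention group, while the ethics section says that controls will receive the intervention with the same safeguards. Built from the numbered steps, the survey would give control viewers the pre-launch testing of the page but no individual check or correction. Up to about 303 parents could be offered the page, assuming the planned 606 are split equally.

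Two stronger readings are tempting and are not supported. A reader might infer that some control parents left believing seatbelts to be unsafe. The documents show only that this is possible, call it conceivable for a small number of participants, and rate the trial phase as minimal risk. A reader might also want a count of parents affected. Any count would rest on invented viewing and misreading rates. The efficacy results are untouched. This is an inexpensive improvement to participant protection and to the accuracy of the plan.

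**What to change.** Reconcile Setting and Procedures with Ethical considerations:

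- State in both places whether control viewing is optional or automatic.
- Define in the ethics section which safeguards are meant.
- Amend step 6 so that any control parent who opens the enhanced page then receives the existing step 5 questions and clarification, placed after all outcome measures.

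The cost is one survey branch reusing existing content, one sentence of text, and about a minute more for the control parents who open the page.

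If data collection is complete, leave the survey as it was, state what control viewers actually received, and correct the ethics section to match.

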Intervention. The intervention will be the enhanced Transport Canada booster seat material that was developed in the previous phase. The intervention material will be the same as the one for the control group in all respects (font size, formatting, etc.), except that it will contain an introduction explaining, in plain language: (a) seatbelts redirect crash forces to the child's thorax and pelvis; (b) booster seats ensure children wear the seatbelt correctly across the hips and chest; and (c) booster seats, used in combination with the seatbelts, prevent injuries to head, neck, spine, abdomen, internal organs, as well as injuries resulting from ejection. The final version of these introduction and accompanying figures will be decided, based on input from the focus groups.

Outcome measures. The primary outcome measures are perceived safety benefit of booster seats and intention to use them, as assessed by the Booster Seat Attitudes Scale (BSAS).²⁰ The BSAS has been validated and tested in a Canadian sample of parents, and the Benefit and Intent subscales of the BSAS reported good internal consistency (Cronbach's alpha of 0.85 and 0.84, respectively). Secondary outcome measures are information recall (when it is safe to start using a booster seat, how to install it, how to use it, and when it is safe for a child to use only the seatbelt) and self-efficacy (as measured by the Perceived behavioural control subscale of the BSAS; Cronbach's alpha of 0.87), their subjective estimates of the risk reduction afforded by booster seats (from 0 to 100%), their subjective estimate of the impact of the intervention on other parents, time they spend reading the material, clicks on links to additional booster seat information.

UPDATE 27 OF JUNE 2019: Factor validation of the BSAS revealed that using the Benefit subscale actually comprises Perceived Benefit (i.e., understanding that booster seats prevent injuries) and Key Benefit (i.e., understanding that booster seats prevent life threatening injuries to the spine and abdomen). Similarly, the Intent subscale of the BSAS was found to have factors: Intent to Use and Intent to Learn (i.e., intention to attend a car seat clinic or workshop). The projected intent scale, developed for this study also had two factors: Projected intent to use and projected intent to learn. These new subscales constitute the updated outcome measures.

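### A paired test (Wilcoxon signed-rank) is one of three options for comparing two independent arms, with no rule for choosing, and it is unclear whether the June 2019 update replaces it for the 0–100% risk-reduction estimates

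*Combined protocol and SAP*

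**What the plan says.** Under Randomized Controlled Trial, Design, the plan states: "The trial will use a concurrent two-group parallel randomized controlled design". It also gives the reason for a control arm: "The use of a control group is necessary to address threats to validity stemming from repeating observations on the same participants: learning and carry-over", followed by sensitization and demand effects.

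Under Outcome measures, the secondary outcomes include "their subjective estimates of the risk reduction afforded by booster seats (from 0 to 100" per cent).

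Under Analysis, the tests are listed as "Student's t, Wilcoxon Sign and Rank" or Mann-Whitney U (the last name is misprinted). These "tests will be used to compare, across groups, subjective estimates of the impact of the intervention on other parents", together with reading time, link clicks and the "pre- versus post-intervention difference in subjective estimates of the risk reduction afforded by booster seats and by seatbelts". The three tests are alternatives, and nothing says when each is to be used.

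The update of 27 June 2019 in the same section assigns two-tailed t tests to the change in benefit (primary) and in intention, and to peer impact. It then applies the same analysis to the remaining secondary outcomes, with recall and interest in brackets. It does not name the 0–100% estimates or reading time, and it covers link clicks only if they are what interest means.

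**The concern.** The signed-rank test needs pairs, or a single sample of differences. Parents in the two randomized arms are different people and form no natural pairs. The one ready way to run the test on these data is within person, before against after, and that is not the randomized comparison. It would bring back the repeat-measurement problems for which the Design paragraph introduces a control arm.

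The preliminary study in the Theoretical framework section makes this a realistic slip. It used the same test, correctly, on 0–100% ratings from a single pretest-posttest group.

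Two things are at stake for the 0–100% estimates. A within-arm change could be reported as an effect of the enhanced material. And with three tests open and no rule, the choice could follow the data.

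**Working it through.** **1. Which listed outcomes could take a paired test?**

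| Outcome in the list | Measured | Within-person pair? | Named in the update? |
|---|---|---|---|
| Impact on other parents | post only | no | yes, t test |
| Reading time | once | no | no |
| Link clicks | once | no | only if interest means clicks |
| 0–100% estimates | pre and post | yes | no |

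The signed-rank test can therefore be run in a natural way only on the 0–100% estimates, and these are not named in the update.

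**2. The documents' own signed-rank figure.** The preliminary study gives Z = 3.157 and p = 0.002. The two-sided normal p for 3.157 is 0.0016, which rounds to 0.002, so the figure reproduces. The 606-participant calculation concerns the BSAS Benefit subscale and has no bearing on this point.

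**3. What each test estimates.** Let s be a pre-post shift common to both arms and e the extra effect of the enhanced material.
- Within the intervention arm, the signed-rank test responds to s + e.
- Within the control arm, it responds to s.
- A between-arm test on change responds to (s + e) − s = e.

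**4. Illustration.** Inputs: the Participants paragraph gives 606 in total, and Ethical considerations says half do not receive the intervention, so 606/2 = 303 per arm. Assumptions that are not in the documents: normal change scores with SD 1, e = 0, and s from 0 to 0.3 SD. Two-sided 0.05, 2,000 simulated trials per row. Percentage of trials rejecting:

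| s (SD) | Signed-rank, intervention arm | Signed-rank, control arm | Signed-rank, pooled | Mann-Whitney on change | t on change |
|---|---|---|---|---|---|
| 0 | 5 | 5 | 5 | 5 | 5 |
| 0.1 | 40 | 38 | 68 | 5 | 5 |
| 0.18 | 86 | 87 | 99 | 5 | 5 |
| 0.3 | 100 | 100 | 100 | 3 | 4 |

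Hand check with a normal approximation, power ≈ Φ(s√n − 1.96):
- s = 0.1, n = 303: 0.1 × 17.41 = 1.74, and Φ(−0.22) ≈ 0.41.
- s = 0.1, n = 606: 0.1 × 24.62 = 2.46, and Φ(0.50) ≈ 0.69.

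Both agree with the simulation. By step 3, s cancels in the last two columns, so their differences between rows are simulation noise.

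**5. Does the within-person test respond to the intervention?** Yes. With s = 0 and e = 0.25 SD, it rejects in 99% of trials in the intervention arm and in 86% pooled. The between-arm Mann-Whitney and t tests reject in 87% and 88%. The within-person test detects e but cannot separate it from s.

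**6. Arbitrary cross-arm pairing.** Matching parents across arms at random kept the error rate at 4% to 5%, but the pairs mean nothing and the result would depend on how they were drawn.

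**The case against.** The strongest reply is that the sentence asks for a comparison across groups and already takes a pre-post difference as the quantity compared. Two of its three tests do exactly that and hold their error rate. A within-arm test would depart from the sentence as written. This stands: the plan permits an unsuitable option and does not commit to it.

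Three stronger readings are tempting, and the documents do not support them.

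- *The signed-rank test would pick up carry-over and not the intervention.* A reader might infer this from the Design paragraph. But the test measures total change: any intervention effect, the Transport Canada content both arms read, and repeat-measurement effects. Step 5 shows that it responds to the intervention.
- *The three-test list certainly still governs the 0–100% estimates.* The update's reference to the remaining secondary outcomes could cover them, although the bracketed examples point the other way. The update under Outcome measures says the new subscales make up the updated outcome measures, so the estimates may even have been dropped. The text allows a t test, the old list or removal.
- *The preliminary study shows how far re-asking alone moves ratings.* Its Z gives 3.157/√312 = 0.179, which is the scale behind the 0.18 row. But its second question was deliberately reworded to list specific injuries, and intervening questions were placed to weaken the influence of the first. The respondents were child seat technicians, researchers and professionals in child passenger safety, not a parent sample. It does not measure the effect of repetition, and the 0.18 row is not a forecast for this trial.

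**Conclusion.** The point holds in a limited form. A paired test is listed for comparing independent arms, no rule chooses among the three tests, and the update leaves the analysis of the 0–100% estimates unclear. If the signed-rank test were used within person, its result would confound any intervention effect with whatever moved both arms.

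The size of that confounding cannot be stated, because the documents give no figure for a common shift in parents. Over an assumed range of 0 to 0.3 SD, false rejection within one arm runs from 5% to nearly 100%. These values rest on normal change scores and 303 per arm.

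The consequence is minor. It reaches secondary outcomes only, and the updated primary analysis uses two-tailed t tests on change between arms.

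**What to change.** Delete the signed-rank test from the between-arm comparisons. State whether the 0–100% estimates remain an outcome and, if so, name one between-arm analysis. The preferred choice is linear regression of the post estimate on arm and pre estimate. With equal pre and post variances and pre-post correlation ρ, the variance of its arm effect relative to an unadjusted change-score comparison is (1 + ρ)/2, which never exceeds 1. If a rank method is preferred, use the Mann-Whitney test on the pre-post difference. Name one test for reading time and for link clicks in the same place.

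Because the update is written in the past tense, also state which test was used for these estimates if they have already been analysed.

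The cost is a sentence or two in the Analysis section. No new data are needed, since the planned pre-post difference already requires the pre estimate.
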